Dance is increasingly becoming a popular form of exercise intervention for individuals with Parkinson disease (PD)[10-12] and dementia[13-16]. Dance is an aerobic exercise that challenges balance and involves functional transitions. In addition learning dance sequences is cognitively challenging. Dance is a structured, multicomponent exercise that can be higher intensity and thus fulfills the criteria laid out by Kirk-Sanchez et al. (2014) of qualities of an exercise program likely to bring about change in cognitive function.[3] In individuals with Parkinson disease and dementia it has been shown to improve motor function.[10-12, 14-16] In individuals with PD studies have shown improvement in cognitive function as measured by MoCA[11, 12], the Brooks spatial task[12], reverse corsi block test of working memory,[12], frontal assessment battery at bedside and mental rotation task[10]. The only study examining impact of dance on cognition in individuals with dementia showed slight improvement in mini-mental status exam scores.[16]

Music is an integral part of dancing and as such its impact on cognitive and behavioral function must be considered. Studies show that listening to music activates specific areas of the brain, most associated with emotional behaviors.[17] Areas activated are the insular and cingulate cortex, hypothalamus, hippocampus, amygdala and prefrontal cortex.[17] Listening to music has been shown to impact behavior and evoke reminiscing in individuals with dementia.[18] Given its potential impact on neural function we propose to include a control group who will listen to live music performances in a group setting. The control group is proposed to elucidate potential benefits of group socialization and music and differentiate these from the potential benefits of the dance training.

We hypothesize that a structured dance program involving novelty and learning of sequences will improve both motor and cognitive function in individuals with mild to moderate dementia greater than a control intervention of social music listening. Aims of this study are to investigate the impact of dance training on 1.) Functional movements such as sit to stand transfers and walking; 2.) Balance; and 3.) Cognitive function in individuals with mild to moderate dementia.

METHODS

Ninety individuals with a diagnosis of mild to moderate dementia will be recruited to take part in the study. Participants will be equally distributed into a dance training group or a

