 The mini BESTest is a clinical balance assessment tool that aims to target and identify 6 different balance control systems that has been shown to be valid and reliable in the elderly[21]. It takes 10 15 minutes to administer and involves tests static and dynamic balance and includes the TUG cognitive.
- Activities and Function Functional Rating Scale of Symptoms of Dementia (care partner fills out)
 - A scale in which the caregiver rates the ability of the individual with dementia to perform daily care activities, memory and sleep.[22]
- Caregiver burden Caregiver Burden Scale
 - A survey tool that is a valid and reliable measure to assess perceived burden among people caring for others with disabilities.[23]

Intervention:

The dance class will be a 90 minute group class held 2 times per week for 12 weeks. Class will consist of seated warm up and stretching routines followed by seated dance that becomes progressively more challenging and leads into standing dance activities. Each participant will stand behind their chair so that the chair can be used to assist with balance. Dance activities initially comprise simple one step moves and progress to more complex sequences. Sequences will be carried over session to session to promote learning of longer sequences. The dance class will be taught by a trained dance instructor who has experience in teaching dance to individuals with neurodegenerative diseases.

The control group will meet one time per week for 90 minutes and will listen to live music performances. These performances are held in the community room of a local senior care living facility and include residents of the senior care community. Control participants will attend with their caregivers and will have opportunity to socialize with other study participants as well as members of the senior care community. Music style and type varies week to week and is chosen to be appropriate to individuals over 65 years of age.

Statistical Analysis:

We calculated the number needed based on previous studies and arrived at 15 per group. Given there is an expectation that some subjects will be found to not meet the

inclusion criteria when given the mini mental status exam equivalent after consenting and that some individuals may drop out we are asking for permission to enroll a maximum of 45 participants in each group. Once each group has 15 individuals actively participating we will stop enrollment

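### The plan cannot separate dance from social contact and music as the control intends; the 2:1 difference in scheduled contact is one documented reason

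*Combined protocol and SAP*

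**What the plan says.** The relevant text is in the background, the Intervention section and the Statistical Analysis section of the combined protocol and SAP.

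- **Purpose of the control (background).** The control is meant to bring out any benefit of socialising in a group and of music, and to "differentiate these from the potential benefits of the dance training".
- **Why music matters (background).** "Music is an integral part of dancing and as such its impact on cognitive and behavioral function must be considered". The plan adds: "Listening to music has been shown to impact behavior and evoke reminiscing in individuals with dementia".
- **Hypothesis (background).** Dance is expected to improve motor and cognitive function "greater than a control intervention of social music listening".
- **Dance schedule (Intervention).** "The dance class will be a 90 minute group class held 2 times per week for 12 weeks".
- **Control schedule (Intervention).** "The control group will meet one time per week for 90 minutes and will listen to live music performances". The number of weeks is not given.
- **Control setting (Intervention).** "These performances are held in the community room of a local senior care living facility and include residents of the senior care community". Also: "Control participants will attend with their caregivers and will have opportunity to socialize with other study participants".
- **Analysis (Statistical Analysis).** Each outcome gets a one-way ANOVA between groups, or a Kruskal-Wallis test, with Bonferroni comparisons. No term for sessions or minutes is mentioned.

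**The concern.** A control can isolate dance only if the other ingredients it shares with the dance programme are delivered to a comparable degree. Here the amount of scheduled group contact differs by design between the groups, and the plan gives no reason for bringing control participants together half as often. The background itself treats music as potentially active on cognition and behaviour, so these ingredients cannot be set aside as inert.

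What is at stake is the conclusion. If the dance group does better on the MoCA, a primary outcome, the purpose sentence invites the reading that dance did it, over and above company and music. The plan has no means of supporting that reading.

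**Working it through.** **Inputs.** Dance: 90 minutes, 2 sessions a week, 12 weeks (Intervention). Control: 90 minutes, 1 session a week, weeks not stated (Intervention). Intermediate assessment at week 6 (Outcome Assessment). The plan gives no total contact time of its own to reproduce.

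**Step 1: scheduled contact.** Contact = minutes per session × sessions per week × weeks.

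| Period | Dance | Control | Ratio |
|---|---|---|---|
| One week | 90 × 2 = 180 min | 90 × 1 = 90 min | 180 / 90 = 2 |
| To week 6 | 180 × 6 = 1,080 min = 18 h | 90 × 6 = 540 min = 9 h | 2 |
| To week 12 | 180 × 12 = 2,160 min = 36 h | 90 × 12 = 1,080 min = 18 h | 2 |

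The weekly row comes straight from the plan. The week 6 row assumes that the control runs at least that long, and the week 12 row that it runs 12 weeks. The hours only restate the weekly ratio.

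**Step 2: does 2:1 in minutes mean 2:1 in music or social exposure?** Let s be the exposure in one control session divided by that in one dance session. The weekly dance-to-control ratio is then 2/s. With purely illustrative values:

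- s = 0.5: 2 / 0.5 = 4
- s = 1: 2 / 1 = 2
- s = 2: 2 / 2 = 1
- s = 3: 2 / 3 = 0.67

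Nothing in the plan bounds s. Control sessions are devoted to live music, with company present. Neither the music content nor the socialising time of the dance class is stated. Music and social contact would each have their own s, and these could fall on opposite sides of 2. Which group has more of either is therefore unknown.

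**Step 3: can the analysis separate contact from dance?** There are two groups, and scheduled minutes take one value in each. A term for scheduled minutes would coincide exactly with group, so it could not be estimated alongside it. No third arm varies contact without dance.

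**Step 4: what else differs?** The control description includes a senior care community room, residents and accompanying caregivers. The dance description mentions none of these, and includes a trained instructor. Equal minutes would leave these differences in place.

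**Step 5: which outcomes?** The background names an effect of music on cognitive and behavioural function. That bears most directly on the MoCA. The plan states no music or social effect on the motor outcomes.

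**The case against.** The strongest reply is that the hypothesis compares a dance programme with social music listening, and that this comparison can be made as scheduled. That is right, and the point does not touch the hypothesis. A related reply is that the background favours intensive, prolonged exercise, so a high dose belongs to the dance programme. That explains two dance classes a week. It does not explain one control session a week, and it does not rescue the claim to separate dance from the rest.

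Four stronger readings are tempting, and the documents do not support them:

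- *Dance participants get twice the music and social contact, so the bias favours dance.* Only scheduled minutes are 2:1. Step 2 shows that exposure could be higher in either group.
- *The gap in minutes is the sole cause, so matching the schedules would cure it.* Setting and the people present would still differ.
- *All outcomes are equally affected.* The plan documents a music effect for cognition and behaviour, not for movement or balance. The split is not perfectly clean, since the motor primary outcome includes a counting task.
- *The chance of a falsely positive result for dance can be calculated.* That would need an assumed benefit per session and an assumed dose-response shape, and the plan gives neither.

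Allocation that yields to a strong preference (Methods) is a separate problem, which also bears on the programme-level comparison. The point here does not rely on it.

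**Conclusion.** The point stands in a limited form. The stated purpose of separating dance from socialising and music is not achievable under the plan. The documented size is a 2:1 ratio of scheduled group contact, 180 against 90 minutes a week. This is one reason alongside setting and caregiver and resident presence. It matters most for the MoCA.

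The schedule figures need no assumption; the cumulative hours depend on how long the control runs. No bias size or direction is claimed. The trial can still say whether the two programmes differed. It should correct what it says such a difference would mean.

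**What to change.** Keep the hypothesis, and keep the aim of describing social and music benefits. Replace only the separating clause of the purpose sentence, for example with:

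> The trial compares a twice-weekly dance programme with once-weekly social music listening. A difference will be attributed to the programme as a whole, and not to dance separately from contact time, social contact and music.

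Carry the same limit into the conclusions. It would help to state the control's duration in weeks in the same edit.

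The cost is a sentence or two of text and a narrower claim. No visits or participants are added.

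A second weekly music session is optional. It would equalise scheduled minutes if the control ran the same 12 weeks, and the wording above would then say twice-weekly for both groups. It needs one more live performance a week (12 over 12 weeks), adds burden for control participants and their caregivers, and may not be in the investigators' power to schedule. It would not restore full attribution, so the limit on the conclusions would still be needed.
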